# 8.6.10 Clinical Laboratory Evaluations

Clinical laboratory data will be first analyzed using International System of Units (SI). Analyses will be repeated using US conventional units. In addition, further analyses on specific laboratory parameters will be performed as described in Sections 8.6.10.1 and 8.6.10.2. The analysis population for each laboratory test is restricted to treated participants who underwent that laboratory test.

# **Summary**:

The number (%) of participants with the following will be summarized using the worst CTC grade on-treatment per participant.

- Post-baseline grade
- Shift table of worst on-study CTC grade compared to baseline CTC grade (grade change from baseline)

# **Listing**:

A by-participant listing of these laboratory parameters will be provided. Laboratory abnormality criteria and laboratory results outside of normal range will be listed. Differences between the SI and US grades will also be provided.

# 8.6.10.1 Abnormal Hepatic Test

#### **Summary:**

The number of participants with the following laboratory abnormalities from on-treatment evaluations will be summarized:

- ALT or AST > 3 x ULN, > 5 x ULN, > 10 x ULN and > 20 x ULN
- Total bilirubin > 2 x ULN
- Concurrent (within 1 day) ALT or AST > 3 x ULN and total bilirubin > 2 x ULN
- Concurrent (within 30 days) ALT or AST > 3 x ULN and total bilirubin > 2 x ULN

# Figure:

- Scatter plot of Total bilirubin peak vs AST peak
- Scatter plot of Total bilirubin peak vs ALT peak

On-treatment peak total bilirubin and on-treatment peak AST/ALT may or may not happen on the same day of liver testing.

# Listing:

A by-participant listing of these specific abnormalities will be provided.

# 8.6.10.2 Abnormal Thyroid Test

# **Summary:**

The number of participants with the following laboratory abnormalities from on-treatment evaluations will be summarized by part, dose level, and overall:

- Elevated TSH value > ULN and
  - with baseline TSH value < ULN

  - with at least one FT3/FT4 test value < LLN within 2-week window after the abnormal TSH test

  - with all FT3/FT4 test values ≥ LLN within 2-week window after the abnormal TSH test
  - with F3/F4 missing within 2-week window after the abnormal TSH test
- Low TSH < LLN and
  - with baseline TSH value > LLN
  - with at least one FT3/FT4 test value > ULN within 2-week window after the abnormal TSH test
  - with all FT3/FT4 test values ≤ ULN within 2-week window after the abnormal TSH test
  - with F3/F4 missing within 2-week window after the abnormal TSH test

# **Listing:**

A by participant listing of these specific abnormalities will be provided.

# 8.6.11 Vital Signs and Physical Findings

# **Listing**:

- Abnormal findings from the physical exam (long form)
- Vital signs
- Height, body weight, BMI, and ECOG performance status
- Pulse oximetry
- All 12-Lead ECG results
- ECG abnormalities
- Pregnancy testing

# 8.6.12 Other Observations Related to Safety

### **Summary:**

- Summary statistics of blood creatinine
- Frequency statistics of renal function
- Frequency statistics of bladder hemorrhage
- Frequency statistics of cytokine release syndrome

# Listing:

- Other adverse events of special interest (AEOSI) consist of a list of PTs grouped by specific category (eg, Guillain-Barre Syndrome, etc.). These are rare events so this analysis will only be performed for the CSR or final analysis, whichever occurs first, unless emerging data suggests otherwise. The dictionary for nivolumab which is most current at the time of analysis will be used and additional categories may be added if deemed relevant for BMS-986277. The dictionary list will along with an event-level listing will be provided.
- Cytokine release monitoring data will be listed by part, dose level, participant ID, and date/time, subject to data availability.
- Diagnostic/Medical procedures

# 8.7 Pharmacokinetic Analyses

All available blood/serum concentration-time data from participants who receive BMS-986277 and/or nivolumab will be reported by part, dose level, and treatment for BMS-986277 and nivolumab, separately. All available derived PK parameter values described in Sections 5.2.2 and 5.3.3 will be included in the PK dataset and reported for the Pharmacokinetic population for BMS-986277 and Pharmacokinetic population for nivolumab, respectively. Only participants with adequate PK profiles will be included in summary statistics and statistical analysis.

#### 8.7.1 Pharmacokinetic Concentrations

#### **Summary:**

Summary statistics will be provided for blood/serum concentrations for each treatment by part, dose level, and nominal collection time.

- Blood concentrations of BMS-986277
- Serum concentrations of nivolumab

Summary statistics will also be tabulated for trough concentrations by study day, for each analyte.

### Figure:

Plots of individual concentration profiles over time as separate plots for each participant and altogether in one figure will be provided. Plots of mean (and standard deviation) concentration profiles versus time will be presented by part and dose level, with different graphical annotations for each study treatment on the same plot.

#### Listing:

- BMS-986277 blood concentrations
- Nivolumab serum concentrations

### 8.7.2 Pharmacokinetic Parameters

### **Summary:**

Summary statistics for all parameters described in Sections 5.2.2 and 5.3.3 will be tabulated for BMS-986277 and nivolumab, separately by part and dose level, where data is available.

Geometric means and coefficients of variation will be presented for Cmax, AUC(0-T), AUC(0-8), AUC(0-48), AUC(INF), CLT, Vss, Vz, C48, Css-avg, AI\_AUC, AI\_Cmax, and Ctrough. Medians and ranges will be presented for Tmax. Means and standard deviations will be presented for T-HALF and T-HALFeff.

# Figure:

- For Cmax, AUC(0-T), AUC(INF), AUC(0-8), AUC(0-48), scatter plots vs dose for each cycle measured; dose proportionality based on a power model and a CI around the power coefficient
- To evaluate the steady state of BMS-986277 concentration in the body, the geometric mean of Ctrough vs. cycle will be plotted by part and dose level with individual participant measurements superimposed on the plots.
- If there are at least 5 participants in an indication and if dose proportionality has been established, then the dose normalized Ctrough values may be presented graphically by indication in order to explore a potential effect of tumor on BMS-986277 pharmacokinetics.

# **Listing:**

• All individual PK parameters will be listed including any data points excluded from analysis.

# Statistical Analysis of Dose Proportionality in Monotherapy Dose Escalation

To assess the dose proportionality, the power model described by Gough et  $al^{12}$ .

PK Parameter =  $A*Dose\beta$ 

will be estimated by the simple linear regression of the natural log of the PK Parameters Cmax, AUC(0-T), and AUC(INF) of BMS-986277 in blood on the natural log of Dose:

 $E[log(PK Parameter)| Dose] = \alpha + \beta * log(Dose).$ 

A slope ( $\beta$ ) equal to 1 would indicate perfect dose proportionality. For each PK parameter (Cmax, AUC(0-T), and AUC(INF)), the point estimates and 90% CI of the slopes will be provided.

As this study is neither optimally designed nor powered to confirm the presence or absence of meaningful departures from dose proportionality, these results should be interpreted with caution. Plots of individual BMS-986277 PK parameter (Cmax, AUC(0-T), and AUC(INF)) values versus dose with fitted regression line on a log-log scale will be presented.

# 8.8 Immunogenicity

To evaluate the incidence of ADA, the following analyses will be performed.

[figure not shown]
# **Summary:**

The number (%) of participants with the following ADA responses will be reported by part, dose level, and overall based on the Immunogenicity population for each treatment.

- Baseline ADA-positive
- ADA-positive
  - Persistent Positive (PP)
  - Not PP Last Sample Positive
  - Other Positive
- ADA-negative

# **Listing:**

• All collected immunogenicity data will be listed with flags indicating baseline-positive sample, ADA-positive sample or ADA-negative sample.

### **CONVENTIONS**

#### 9.1 **General Conventions**

- All statistical analyses will be carried out using SAS (Statistical Analysis System software, SAS Institute, North Carolina, USA) unless otherwise noted.
- In general, the BMS Global Standard time windowing, imputation rules, and counting rules will be applied.
- The following conversion factors will be used to convert days to months or years.
  - 1 month = 30.4375 days
  - 1 year = 365.25 days
- Duration (eg, duration of response) will be calculated as follows:
  - Duration = (Last date first date + 1)
- Last known date alive will be defined based on all appropriate dates collected on the CRF.
- Safety data will be handled according to the BMS safety data conventions. This document includes descriptions on how to analyze AE data as well as how to handle partial dates, missing dates, and unknown end dates when analyzing safety data.

#### 9.2 **Multiple Measurements**

# **Adverse Events**

The algorithm for collapsing adverse event records is using the following conventions:

For each participant and specified category, the corresponding adverse event records will be collapsed when:

- Multiple adverse event records have the same onset date.
- The onset date of an event record is either the same day or 1 day later than the resolution date of a preceding event record (contiguous events).
- The onset date of an event record is after the onset date and prior to or on the resolution date of a preceding event record (overlapping events).

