- d A minimum of 24 hours is required between doses during sequential dosing weeks (eg, C1D1-C1D5; C2D1-C2D5). Infusions of BMS-986277 on Day 3 and Day 5 must be administered within 7 days of Day 1.
- e EOT visit is C26D29 ( $\pm$  7 days) or at the time of study treatment discontinuation. If within 7 days prior to FU Visit 1, the EOT visit may be skipped and FU Visit 1 should be completed and include all EOT biomarker samples.

**Table 2-5: On-Treatment Assessment Schedule (Monotherapy Expansion - BMS-986277 [Part 3 Cohort 3] Monotherapy with Option for Subsequent Nivolumab Therapy)(CA034001)**

Procedures a	Cycle 1 (28 days) b				Cycle 2 (28 days) b				Optional: Cycle 3 and each subsequent cycle (28 days; Nivolumab only) c			Notes		
	D1 d	D3 d and D5 d	D8 ( $\pm 3$ days)	D15 ( $\pm 3$ days)	D22 ( $\pm 3$ days)	D1 d ( $\pm 3$ days)	D3 d and D5 d	D8 ( $\pm 3$ days)	D15 ( $\pm 3$ days)	D22 ( $\pm 3$ days)	D1 ( $\pm 3$ days)		D15 ( $\pm 3$ days)	EOT e
	Safety	■	■	■	■	■	■	■	■	■	■		■	■
Targeted PE, Physical Measurements, Vital Signs, ECOG Performance Status	X	X	X	X	X	X	X	X	X	X	X	X	X	On each BMS-986277 dosing day, assessments (vital signs) will be performed at predose and every 15 minutes ( $\pm 5$ minutes) until 60 minutes following completion of infusion and then at 4 hours ( $\pm 30$ minutes) and 8 hours ( $\pm 1$ hour) postdose. See note in Table 2-1. On each nivolumab dosing day, vital signs will be performed at predose only.

**Table 2-5: On-Treatment Assessment Schedule (Monotherapy Expansion - BMS-986277 [Part 3 Cohort 3] Monotherapy with Option for Subsequent Nivolumab Therapy)(CA034001)**

Procedures a	Cycle 1 (28 days) b				Cycle 2 (28 days) b				Optional: Cycle 3 and each subsequent cycle (28 days; Nivolumab only) c			Notes		
	D1 d	D3 d and D5 d	D8 ( $\pm$ 3 days)	D15 ( $\pm$ 3 days)	D22 ( $\pm$ 3 days)	D1 d ( $\pm$ 3 days)	D3 d and D5 d	D8 ( $\pm$ 3 days)	D15 ( $\pm$ 3 days)	D22 ( $\pm$ 3 days)	D1 ( $\pm$ 3 days)		D15 ( $\pm$ 3 days)	EOT e

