Dosing Schedule per Protocol	Sequential dosing on Days 1, 3, and 5 in a 28 day cycle for up to 3 cycles	480 mg on Day 15 in a 28 day cycle for up to 26 cycles
Duration of Therapy	Duration of therapy (weeks) = (last dose date of BMS-986277 - first dose date of BMS-986277 + 24) / 7 (Note: 24 days is the time between Day 5 and Day 29)	Duration of therapy (weeks) = (last dose date of nivolumab - first dose date of nivolumab + 28) / 7
Dose	Dose (vp) is defined as total dose administered in vp/dose at each dosing date as collected on the CRF.	Dose (mg) is defined as total dose administered in mg at each dosing date as collected on the CRF.
Cumulative Dose	Cum dose (vp) is sum of the doses (vp) administered to a participant.	Cum dose (mg) is sum of the doses (mg) administered to a participant.
Relative Dose Intensity	RDI (%) = {cumulative dose (vp) / [(duration of therapy (weeks) x 3 x number of cycles x planned* dose (vp)) / (number of cycles x 4 weeks)]} x 100	RDI (%) = {cumulative dose (mg) / [(duration of therapy (weeks) x number of cycles x 480 mg) / (number of cycles x 4 weeks)]} x 100

Table 7: Study Therapy Parameter Definition for Parts 2 and 3

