# 8.6.8 Exposure-Adjusted Adverse Events

Analyses that take into account the multiple occurrences of a given AE will be conducted. In order to prepare these analyses, the CRF data will be processed according to standard BMS algorithms  in order to collapse AE records into unique records based on the PT. This data will be presented as the rate per 100 patient-years. These analyses will take into account all on-treatment events (allowing more than 1 event per participant) and the total duration of AE follow-up that is based on exposure to the study medication(s), defined as the first dose of either study treatment to last dose of either study treatment. The patient-years will be computed as the sum over the participants' follow-up expressed in years and is defined as:

- Date of last dose of either study treatment date of first dose of study treatment + 100 + 1 days, for participants who are off study treatment and were followed for at least 100 days after the last dose of either study treatment.
- Last known alive date date of first dose of study medication +1, for participants who are still on treatment or who are off study treatment and were followed less than 100 days after the last dose of either study treatment.

When specified the 95% CI of the rate per 100 person-year of exposure will be derived using normal approximation and variance estimation proposed in Cook and Lawless.

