### Listing:

• Unique instances of all AEs, ie, after duplicates have been eliminated and overlapping and contiguous occurrences of the same event (ie, same PT) have been collapsed.

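### The adverse-event collapsing rule can merge reactions to successive infusions, so the repeat-event rate for an acute post-infusion term may be understated by up to two thirds

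*SAP*

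**What the plan says.** SAP 8.6.8 states its purpose plainly: "Analyses that take into account the multiple occurrences of a given AE will be conducted". More than one event per participant is allowed, and results are given per 100 patient-years. Before counting, the data are processed "in order to collapse AE records into unique records based on the PT". The accompanying listing shows events "after duplicates have been eliminated and overlapping and contiguous occurrences of the same event (ie, same PT) have been collapsed".

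SAP 9.2 gives the algorithm. "For each participant and specified category, the corresponding adverse event records will be collapsed when" one of three conditions is met:

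- the records share an onset date;
- the later onset is "either the same day or 1 day later than the resolution date of a preceding event record (contiguous events";
- the later record begins while the earlier one is still open, up to and including the day the earlier one resolves (the overlapping condition).

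All three compare calendar dates. None asks whether a dose was given between the two records.

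On dosing, SAP Table 7 gives, for Parts 2 and 3, "Sequential dosing on Days 1, 3, and 5 in a 28 day cycle". Protocol 7.1.4 to 7.1.6 use the same days for up to 2 cycles. Protocol 7.1.3 gives Part 1 one dose on Day 1, then doses on Days 15, 17 and 19, and on Days 1, 3 and 5 of Cycle 2. The spacing may be shortened: "A minimum of 24 hours is required between doses during sequential dosing weeks" (Protocol Table 2-3, footnote d).

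**The concern.** The one-day tolerance in the contiguous rule coincides with the dosing interval. If a fever starts on Day 1 and resolves on Day 2, a new fever after the Day 3 infusion begins exactly one day after resolution, and the two become one record. A Day 5 fever joins the same chain if the Day 3 fever also lasted to the next day.

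Next-day resolution is plausible. The rule ignores clock time, and the protocol expects delayed effects: vital signs to 8 hours after each dose, optional cytokine sampling to 12 hours, and observation for up to 12 hours (Tables 2-2 to 2-5, 7.4.5, 9.4.1). A reaction some hours after an afternoon infusion can pass midnight.

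Infusion reactions and cytokine release are named risks in protocol 7.4.5, and antipyretic prophylaxis is given on every BMS-986277 dosing day. The incidence tables count a participant once per PT and so cannot show recurrence. SAP 8.6.8 is the tabulated output that could. At stake is whether it separates a participant who reacts to each infusion in a dosing week from one who reacts once.

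**Working it through.** The documents state no event count or rate for this point, so there is no printed figure to reproduce. The check applies the three SAP 9.2 conditions to records of one PT.

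**Inputs from the documents**
- Parts 2-3: study days 1, 3, 5, 29, 31, 33 (6 infusions).
- Part 1: study days 1, 15, 17, 19, 43, 45, 47 (7 infusions).
- Minimum spacing: 24 hours.

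**Inputs assumed** (the documents give neither)
- p: probability that an infusion causes the reaction, with onset on the infusion day.
- q: share of reactions that resolve the next day; the rest resolve the same day.

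**Step 1. One dosing week on Days 1, 3, 5, with a reaction to every infusion**
- All resolve the same day: the next onset is 2 days after resolution; 3 events stay 3.
- Exactly one of the first two lasts to the next day: 3 become 2.
- All last to the next day: 3 become 1, a fall of 2/3 = 66.7%.

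**Step 2. Whole-course ceiling (p = 1, q = 1)**
- Parts 2-3: 6 become 2; fall 4/6 = 66.7%.
- Part 1: 7 become 3; fall 4/7 = 57.1%. The lead-in dose is 14 days from the next and does not merge.
- With the SAP's longer cycle counts (up to 3 cycles in Parts 2-3; 3, optionally 6, in Part 1): 9 become 3 (66.7%), 10 become 4 (60.0%), 19 become 7 (63.2%).

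**Step 3. Intermediate cases at 48-hour spacing**
The protocol schedule has four adjacent dose pairs in each setting (two per three-dose week). A pair merges when both doses cause a reaction and the first lasts to the next day, with probability p²q. Expected events lost are therefore 4p²q.
- Parts 2-3: fall = 4p²q / 6p = 2pq/3.
- Part 1: fall = 4p²q / 7p = 4pq/7.

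| p | q | Parts 2-3 | Part 1 |
|---|---|---|---|
| any | 0 | 0% | 0% |
| 0.4 | 0.5 | 13% | 11% |
| 0.7 | 0.5 | 23% (4.2 to 3.22) | 20% (4.9 to 3.92) |
| 0.7 | 1 | 47% (4.2 to 2.24) | 40% (4.9 to 2.94) |
| 1 | 1 | 67% | 57% |

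**Step 4. Other spacings within one dosing week**
- Days 1, 2, 3, same-day resolution, p = 0.7: expected true events 2.1; lost 2 × 0.49 = 0.98; fall 46.7%.
- Days 1, 2, 3, next-day resolution, p = 0.7: Days 1 and 3 also merge when Day 2 is free of a reaction, adding 0.7 × 0.3 × 0.7 = 0.147; lost 1.127; fall 53.7%.
- Days 1, 4, 7: no merging with same-day or next-day resolution.

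**Step 5. From counts to rates**
Patient-years in SAP 8.6.8 depend only on dosing and follow-up dates, so the PT's rate falls by the same proportion as its count. The all-AE rate is diluted. If such records are 10%, 25% or 50% of all AE records, the ceiling fall is 2/3 of that share: 6.7%, 16.7% or 33.3%.

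**The case against.** The rule is a standard way to stop grade changes in one continuing event being counted as new events, and it harms nothing unless reactions last into the next day or doses are compressed. The documents give no reaction duration, so every figure between zero and the ceiling is assumed. A reader might infer that three reactions in a dosing week always become one event. That is not supported: at 48-hour spacing, same-day resolution loses nothing, and doses may also be spread further apart. Fever and chills, being separate PTs, do not merge with each other in this analysis.

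The affected output is also limited. SAP 8.6.8 has no per-infusion element. Its once-or-multiple table covers select AEs only, and the select list for BMS-986277 may not exist. A participant who reacts in both cycles would still be classed as having multiple events. Incidence and worst-grade tables (SAP 8.6) and DLT tabulation (8.6.1) do not use collapsed counts, and all recorded AEs, vital signs and cytokine data are listed (8.6.6, 8.6.11, 8.6.12). A reader might infer that the primary safety endpoint or the dose-escalation model is compromised; neither is. Nor do the unequal losses by part distort a planned comparison: the gap is 3 percentage points in the middle case, and no formal between-part comparison of event rates is specified.

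Two further cautions are fair. The cited sponsor algorithms are not available here and might treat new infusions separately, although the rule printed in 9.2 does not. An exception covering every PT and both drugs would split continuing events re-recorded at dosing visits.

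These points limit the size of the finding and the scope of the remedy. They do not remove the mismatch: a listing does not correct a tabulated rate, and the rule as printed undercounts the repeats that 8.6.8 sets out to count.

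**Conclusion.** The point stands in conditional form and should be addressed. Following SAP 9.2 as printed merges same-PT reactions to successive infusions when they resolve on the next calendar day, or even on the same day if doses are given on consecutive days. For an affected PT the understatement ranges from zero to 67% in Parts 2-3 and 57% in Part 1 on the protocol schedule. The 23% and 20% figures rest on assumed values (p = 0.7, q = 0.5), on independence between infusions, and on onset on the infusion day. The mechanism and the ceilings follow directly from the documents; how often it will occur cannot be known from them. The consequence is confined to the exposure-adjusted repeat-event analysis and its collapsed listing.

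**What to change.** In SAP 9.2 and 8.6.8, prespecify a short list of acute post-infusion PTs (for example pyrexia, chills, infusion related reaction, cytokine release syndrome). For these PTs only, do not collapse two records when a BMS-986277 infusion was given on or after the resolution date of the first and on or before the onset date of the second. Two clarifications are needed:

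- The exception takes precedence over the contiguous and overlapping conditions when the second onset falls on the first's resolution date. Otherwise the overlapping condition would merge the records again.
- The qualifying infusion is dated after the onset of the first record, so that the infusion preceding the first reaction cannot itself trigger the exception.

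All other PTs keep the standard rule, as do overlapping records in which the first had not resolved before the infusion date. In the Day 1, 3, 5 example with next-day resolution, three reactions then count as three.

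Alternatively, keep the standard algorithm throughout and show uncollapsed counts for the listed PTs beside the collapsed ones.

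The cost is a few lines of SAP text, a PT list fixed before database lock, and one extra condition in the program, using infusion dates already on the CRF. The downside is small: a few continuing events recorded in two pieces across an infusion would be counted twice.

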# **Laboratory Measures**

For tabulations of changes from baseline the following will be used, in a hierarchical sequence, to select the post-treatment measurement included in the analysis (if a criterion does not apply it would be skipped in the sequence):

- If multiple laboratory measurements are obtained within the same scheduled time frame, then the measurement obtained on the time closest to the target time/day will be used;
- If more than one value meets the above criterion, then the measurement obtained on the earlier time will be used;
- For tabulations by CTC grade and summarized by worst toxicity grade, if multiple laboratory measurements are obtained within a analysis period (post-baseline), then the worst measurement within the analysis period, respectively, will be used.

